The pharmacokinetics of UFH are unpredictable due to the binding of UFH to a number of plasma proteins, macrophages, and endothelial cells. Additionally, the response varies among patients so it is routine practice to monitor heparin frequently and adjust the dose based on the results of a coagulation test.⁹ The aPTT, a plasma based assay measuring activity of intrinsic and common coagulation pathways, has been the most widely used method to monitor IV UFH. Interestingly, the data that support adjusting heparin doses to maintain a therapeutic aPTT range are based on weak evidence¹¹, and heparin dosing and monitoring has not been rigorously studied in patients with LVADs. The International Society for Heart and Lung Transplantation MCS guidelines recommend titrating heparin to a target aPTT of 60-80 seconds, despite these known limitations.⁵ Although the aPTT is widely available, relatively inexpensive and has gained long term familiarity, many problems with the use of this assay have been identified. The assay is susceptible to physiological and nonphysiological factors that do not reflect intrinsic heparin activity, causing patients to receive unintentionally high or low doses of heparin.¹² Lupus anticoagulant and factor XII deficiency may overestimate the aPTT. Common clinical features of patients with LVADs such as liver disease, consumptive coagulopathy, concurrent warfarin administration and hemolysis may also overestimate the aPTT. On the other hand, low antithrombin levels and elevated factor VIII levels may attenuate the expected aPTT response.¹² Unlike the aPTT assay, the anti-Xa activity assay is a more direct measure of UFH and is unaffected by the presence of lupus anticoagulant, liver disease, or consumptive coagulopathy. Furthermore, in comparison with the aPTT, the correlation between anti-Xa activity and heparin concentration is more robust, the target therapeutic range is better defined, and anti-Xa activity is resistant to variability in the setting of stress and inflammation, which are features of the acute postoperative period. Conversely, this assay is not as widely available as the aPTT, may incur higher costs and may underestimate heparin concentrations in the setting of hemolysis or low antithrombin levels. In addition, elevated triglyceride or bilirubin levels may falsely lower the results.¹³ The known strengths and limitations of both assays make it challenging to determine which method of heparin monitoring is ultimately superior.¹²

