
Previous Research and Preliminary Data

Evidence of superiority of monitoring IV UFH effects with the anti-Xa assay in terms of safety and effectiveness is lacking. Studies have consistently noted the discordance between the aPTT and the anti-Xa assay in various adult and pediatric populations.^{14,15,16,17,18,19,20,21,22,23,24,25,26} In adult patients with LVADs specifically, concordance rates between the assays have been reported as low.^{14,15} Based on four patients with LVADs at our institution (Figure 1.), the average relationship between the aPTT and the anti-Xa assay is shown (solid blue line). The dashed green line represents ideal concordance between the assays. Most of the data points show considerable scatter from both the average (solid black) and ideal (dashed green) relationships. The crude correlation co-efficient (not accounting for repeated measures) is 0.44. When values from both assays fall in the middle rectangle, the assays both suggest that heparin anti-coagulation is in the therapeutic range. Values in the discordant areas occur when information provided by the two assays is discrepant (e.g., one assay suggest therapeutic anti-coagulation, whereas the other suggests sub-therapeutic anticoagulation). Thus, our preliminary data in patients with LVADs at our center suggests that the assays are discordant and that there does not appear to be a precise relationship between the assays. In addition to showing discordance, studies have suggested that monitoring heparin with the anti-Xa activity assay may result in lower heparin exposure, fewer dose titrations, lower cost, and possibly less bleeding.^{14,15,16,17,18,19,20,21,22,23,24,25,26} Although there have been randomized controlled trials in patients who have not had LVADs or other MCS devices,^{17,18} these trials were small, non-blinded, and found no significant differences in bleeding or thrombosis between groups.

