“Therapeutic anticoagulation” is defined as two consecutive monitoring values within the goal range, according to assigned monitoring assay. (either two consecutive aPTT values within 60-94 seconds or two consecutive anti-Xa values within 0.3-0.7 IU/ml)

Secondary Outcomes:

Explore heparin dosing and the concordance between the aPTT and anti-factor Xa activity in this patient population.

“Concordance” is defined when simultaneously drawn aPTT values and anti-Xas values are within the goal range (aPTT within 60-94 seconds and anti-Xa within 0.3-0.7 IU/ml).

Explore clinical outcomes including pump thrombosis, gastrointestinal bleeding, neurological events such as stroke, and major bleeding in this patient population.

C Study Design

Study setting and design

VAD AntiX feasibility study will take place at Barnes-Jewish Hospital, an academic hospital in affiliation with Washington University Medical Center located in the United States. This trial has been designed in accordance with the SPIRIT (Standard Protocol Items: Recommendations for Interventional Trials) checklist³³. The VAD AntiX feasibility study will be a stratified randomized, trial with one specific aim: (1) Demonstrate the feasibility of implementing nomograms for heparin administration based on aPTT measurement as well as anti-Xa activity. This feasibility trial will be the foundation for a larger pilot trial and subsequent comparative effectiveness trial that will seek to determine the optimal monitoring method of IV UFH in the perioperative period for LVAD patients.

A heparin nomogram is a tool or table used to standardized heparin administration and dosing when heparin is administered as a continuous infusion. Dosing adjustments are prescribed in the table based on the laboratory results.

Subject Selection

All patients 18 and older undergoing HeartMate II®, HeartMate III® or HeartWare®, LVAD implantation at Barnes-Jewish Hospital, St. Louis, Missouri, USA will be eligible for enrollment in this study. This hospital is an academic medical center affiliated with Washington University School of Medicine. Patients will be recruited preoperatively and will provide written informed consent. Any patient who is unable to receive heparin [e.g. patients with heparin-induced thrombocytopenia (HIT)] or an anaphylactic allergy to heparin] will be excluded. Patients who develop HIT during the course of the study will remain enrolled and be included in the intention-to-treat analysis.

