weight-based nursing driven heparin nomogram starting at 12 units/kilogram/hour without a bolus. Patients randomized to aPTT monitoring will follow our institution's current nursing-driven aPTT nomogram and the patients randomized to anti-Xa monitoring will follow a nursing-driven anti-Xa nomogram. Each nomogram has instructions regarding scheduled assay lab draws that nurses will follow. Regardless of group allocation, while IV UFH is administered according to one of the two nomograms, both the aPTT and the anti-Xa activity will be determined at specified time points, although clinicians will only receive the information according to group assignment. Clinicians will be instructed not to deviate from the randomized monitoring protocol. All relevant concomitant care, interventions, and laboratory draws will be at the discretion of the ICU and surgical teams as part of routine postoperative care.

Randomization and Design:

Following LVAD implantation, subjects will be randomized via computer-generated randomization by the study coordinator. Patient randomization will be stratified by LVAD type with HeartMate II®, HeartMate III®, and HeartWare® patients being randomized to the 2 nomograms separately by the assigned study coordinator. Randomization will take place within twelve hours after arrival to the ICU and be subsequent to monitoring and management of heparin anticoagulation with either an aPTT or anti-factor Xa based nomogram.

Subjects in this study will be offered the opportunity to participate in the Systematic Assessment and Targeted Improvement of Services Following Yearlong Surgical Outcomes Surveys (SATISFY-SOS #201203008).

aPTT and anti-Xa Nursing Driven IV UFH Nomograms

aPTT Result	Bolus Dose	Infusion Change
aPTT less than 40 seconds	None	Increase 3 units/kg/hour
aPTT 40-50 seconds	None	Increase 2 units/kg/hour
aPTT 51-59 seconds	None	Increase 1 unit/kg/hour
aPTT 60-94 seconds	None	No change
aPTT 95-104 seconds	None	Decrease 1 unit/kg/hour
aPTT 105-114 seconds	Hold infusion for 30 minutes	Decrease 2 units/kg/hour
aPTT greater than 114 seconds	Hold infusion for 1 hour	Decrease 3 units/kg/hour
Draw STAT aPTT 6 hours after each rate change. Once two consecutive aPTT's are therapeutic (60-94 seconds), then draw aPTT every am. Draw CBC Express every 72 hours until heparin is discontinued.		

Anti-Xa Result	Bolus Dose	Infusion Change
Anti-Xa less than 0.2 IU/mL	None	Increase 3 units/kg/hour
Anti-Xa 0.2-0.29 IU/mL	None	Increase 2 units/kg/hour

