aPTT monitoring group: While on fixed-dose heparin (750 units/hr), an aPTT and an anti-Xa will be sent every 6 hours from the same tube (2.7 ml of blood in a light blue top tube). The tube will be sent and processed via standard procedure for the aPTT assay to which the patient is randomized. A paper requisition form and an assigned study ID number will accompany the tube with an order for an anti-Xa that will result in a research profile blinded to the clinical team, but available to the research team. This will be the process for all the subsequent aPTT/anti-Xa lab draws in the aPTT monitoring group. When the clinical team decides to start weight-based heparin dosing, the aPTT heparin nomogram order bundle will be ordered as per standard of care. The process noted above for lab draws and paper requisition forms will apply to the weight-based heparin nomogram as well. The aPTT and anti-Xa will be drawn every 6 hours until two values are in the therapeutic range. Once two values are within the therapeutic range, they will be drawn every 24 hours. All timed lab draws are current standard of care for patients being monitoring on heparin nomograms at BJH.

anti-Xa monitoring group: While on fixed-dose heparin (750 units/hr), an anti-Xa and an aPTT will sent every 6 hours from one tube (2.7 ml of blood in a light blue top tube). Monitoring heparin therapy with this frequency is current standard of care. The tube will be sent and processed via standard procedure for the anti-Xa assay to which the patient is randomized. A paper requisition form and an assigned study ID number will accompany the tube with an order for an aPTT that will result in a research profile blinded to the clinical team, but available to the research team. This will be the process for all the subsequent aPTT/anti-Xa lab draws in the anti-Xa monitoring group. When the clinical team decides to start weight-based heparin dosing (per standard of care), the anti-Xa heparin nomogram order bundle will be ordered. The process noted above for lab draws and paper requisition forms, will apply to the weight-based heparin nomogram

as well. The aPTT and anti-Xa will be drawn every 6 hours until two values are in the therapeutic range. Once two values are within the therapeutic range, they will be drawn every 24 hours. All timed lab draws are current standard of care for patients being monitoring on heparin nomograms at BJH.

Outcomes data

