For feasibility, questionnaires completed by the nursing staff evaluating the practicality and acceptability of the nomograms will be analyzed with descriptive statistics and compared between the two groups using a Chi square test. The percentage of correct dosing adjustments made by the nursing team required to achieve first therapeutic anticoagulation will be compared between the two groups using a Mann Whitney U test. For success, the number of dosing changes required to achieve first therapeutic

anticoagulation, the time (in hours) to achievement of first therapeutic anticoagulation, and the percentage time therapeutic anticoagulation remains after it is achieved will be compared between the two groups using a Student's t-test if data is normally distributed or a Mann-Whitney U test if data is not normally distributed.

If possible based on population size, concordance between groups of aPTT and anti-factor Xa activity will be assessed with a suitable (parametric or non-parametric) mixed effects statistical model. This approach is likely to yield more accurate information than crude correlation assessments that have been used in other studies, which have not taken into account repeated measures within patients. We will use repeated measures ANOVA and Tukey's test for multiple comparisons to analyze heparin administration in the two groups. With a mixed effects model, we will compare heparin dose in the two groups, while controlling for confounders, including the effect of time on the dose of heparin administered, and assuming an autoregressive covariance structure (the nature of the correlations between measurements for the same patient), as well as a random intercept to allow for some of the effect of potential unknown confounders.

If possible based on study size, markers of gastrointestinal bleeding, major bleeding, neurologic events, and thrombotic complications will be compared with a Chi-square test. Additionally, as able, adjusted logistic regression will be used to explore risk factors for complications. We will use intent-to-treat approach in our analyses. We will also use appropriate imputation methods and test the sensitivity of our results. No imputation is planned for missing primary outcomes data.

F Data Handling and Record Keeping

Data Collection and Methods

All questionnaire's performed will be collected and responses recorded.

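### Concordance is defined only as both assays in goal range, so paired results that agree the patient is below or above range are not counted as agreement

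*Combined protocol and SAP*

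**What the plan says.** Section B (Study Objectives, Secondary Outcomes) holds the only definition: concordance "is defined when simultaneously drawn aPTT values and anti-Xas values are within the goal range", with the two ranges given as aPTT 60-94 seconds and anti-Xa 0.3-0.7 IU/mL. No other section widens it.

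Section A (Previous Research and Preliminary Data) describes the centre's plot from four patients. Of the in-range area it says: "When values from both assays fall in the middle rectangle, the assays both suggest that heparin anti-coagulation is in the therapeutic range". Of disagreement it says: "Values in the discordant areas occur when information provided by the two assays is discrepant", and its example is one assay in range and the other below. The crude correlation, ignoring repeated measures, is 0.44.

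Section E (Statistical Plan) says that, if the population size allows, "concordance between groups of aPTT and anti-factor Xa activity will be assessed with a suitable (parametric or non-parametric) mixed effects statistical model". It adds: "This approach is likely to yield more accurate information than crude correlation assessments that have been used in other studies". It names no response variable for this model. The autoregressive covariance and random intercept described next belong to the model for heparin dose.

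Section D (Nomogram intervention procedure) has both assays run on the same tube in both arms, every 6 hours during fixed-dose heparin. On the nomogram the rule is: "The aPTT and anti-Xa will be drawn every 6 hours until two values are in the therapeutic range". After that, draws are every 24 hours.

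**The concern.** Agreement between two assays should not depend on where the patient happens to be. Two results that both call for more heparin agree just as much as two results that both call for no change. Under Section B only the second pair counts. The first is not concordant by Section B and not discrepant in the sense of Section A, so it has no class.

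Such pairs are to be expected. Paired sampling starts on fixed-dose heparin, before weight-based titration, and both nomograms have rows below and above the goal range. Sampling is also denser until values come into range, so a proportion over all draws gives extra weight to out-of-range time.

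If the Section B definition is what gets summarised, a low figure could be read as poor agreement between the assays when part of it is time out of range. Section C calls this trial the foundation for a larger pilot and a comparative effectiveness trial, so the misreading could carry forward.

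**Working it through.** The documents state no concordance rate, so there is no figure to reproduce. The check has a part that needs no assumptions and an illustration that does.

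**1. Ceiling (no assumptions).** P(both in range) ≤ min{P(aPTT in range), P(anti-Xa in range)}. If the assays always fall in the same category, P(both in range) equals the in-range share. With 40% of draws in range, perfect agreement scores 40% by Section B and 100% by same category.

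**2. Illustration.** Inputs:
- Correlation 0.44, from Section A, used here as a latent bivariate normal correlation. It rests on four patients and ignores repeated measures.
- Below/in/above shares: assumed, because the documents give none. Unequal shares are plausible, because Section A says: "Common clinical features of patients with LVADs such as liver disease, consumptive coagulopathy, concurrent warfarin administration and hemolysis may also overestimate the aPTT".
- Denominator: all pairs (assumed).

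Each latent scale is cut at the normal quantiles of the shares, and the nine cell probabilities follow. Both-in is the middle cell, and same category is the sum of the diagonal. Chance is the diagonal expected for unrelated assays, Σ p_k q_k, where p_k and q_k are the two assays' shares. For 50/40/10 it is 0.5² + 0.4² + 0.1² = 0.42.

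| Shares (below/in/above, %) | Both in (Section B) | Both below or both above | Same category | Chance, same category | Linear-weighted kappa |
|---|---|---|---|---|---|
| 50/40/10, both assays | 0.191 | 0.351 | 0.543 | 0.420 | 0.27 |
| 70/25/5, both assays | 0.092 | 0.558 | 0.650 | 0.555 | 0.26 |
| 20/70/10, both assays | 0.517 | 0.109 | 0.626 | 0.540 | 0.24 |
| 20/70/10 and 50/45/5 | 0.338 | 0.167 | 0.505 | 0.420 | 0.19 |
| 20/70/10 and 10/50/40 | 0.354 | 0.118 | 0.472 | 0.410 | 0.17 |

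At one fixed correlation the Section B figure runs from 9% to 52%, largely following the in-range share. Between 11% and 56% of all pairs agree that the patient is out of range and are left out. Same-category agreement runs from 47% to 65%, against 41% to 56% by chance. It is a better description of agreement, but it also depends on the shares: unrelated assays at 70/25/5 (0.555) score higher than assays correlated 0.44 at 50/40/10 (0.543).

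**3. Draw schedule.** Assume 14 days, perfectly agreeing assays, 25% of draws in range during the first 6-hourly period, 70% afterwards, and no return to 6-hourly draws.
- First period 1 day: (4 × 0.25 + 13 × 0.70)/17 = 10.1/17 = 0.594.
- First period 4 days: (16 × 0.25 + 10 × 0.70)/26 = 11.0/26 = 0.423.

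The Section B figure falls by 17 percentage points although agreement is perfect in both cases.

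**4. Precision of kappa.** Simulation with shares 50/40/10, correlation 0.44 and an assumed within-patient correlation of 0.3: the central 95% of weighted kappa estimates is about 0.15 to 0.38 for 20 patients with 17 pairs each. It is about 0.0 to 0.5 for 10 patients with 4 pairs each (one arm, about one day of fixed dose).

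**The case against.** The strongest reply is that the harm depends on an analysis that the plan does not promise. No section says that a concordance proportion will be computed or compared between arms. Section E plans only a mixed model and contrasts it with crude correlation, which points towards continuous paired values. On that reading the Section B category drives nothing and the ceiling does not matter. This stands as a limit on the consequence. It does not remove the defect, because the stated definition of a named secondary outcome still mismeasures agreement, and nothing says the model replaces it.

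A reader might infer that Sections A and B contradict each other. They do not. Section B never calls a both-below or both-above pair discordant, and the figure that might label those areas is not in the text available here. The pairs are unclassified, not classified in two ways.

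A reader might also infer that same-category agreement is immune to dosing and schedule. It is not. In the schedule above at correlation 0.44, with 70/25/5 followed by 20/70/10, it is 63% against 64% for a first period of 1 or 4 days. If the first period is 50/25/25, it is 60% against 55%. Any apparent stability comes from the assumed split of below and above.

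Finally, leaving open the response of an exploratory model in a 20-patient convenience sample is a common level of detail. That gap would not merit a point on its own.

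**Conclusion.** The point holds and is minor. Applied as written, the definition omits pairs that agree the patient is out of range, and any proportion based on it is capped by the share of draws in range. That follows from the definition alone. The sizes (9% to 52% against 47% to 65%) rest on assumed shares, an assumed denominator and a four-patient correlation reused as a latent one, so they are illustrations and not forecasts.

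The effect is confined to the interpretation of an exploratory outcome without a decision rule. The primary feasibility and success outcomes do not use this definition. The raw pairs are recorded, so the matter can be put right at analysis. The documents do not support the stronger conclusion that the trial will report a misleading concordance rate.

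**What to change.** Define a pair as concordant when both assays fall in the same category of their own goal range: below, within or above. Then:
- Report the 3x3 table by arm and by phase (fixed-dose, nomogram). Keep both-in-range as a separate descriptive figure with its denominator stated.
- Beside same-category agreement, report the agreement expected by chance, or weighted kappa with bootstrap intervals that resample patients. Say that it is imprecise with 20 patients and itself depends on the shares.
- State whether the Section E mixed model takes this yes/no response with a patient random intercept, or the continuous paired values. Name the 3x3 table as the fallback if the model cannot be fitted.

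The cost is a few sentences and one table shell, settled before the data are examined. No new data are needed, since both assays already come from the same tube in both arms. The downside is slightly more analysis work and a kappa that cannot carry much weight alone.

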Inclusion criteria:

All patients 18 years of age and older who are undergoing HeartMate II®, HeartMate III® or, HeartWare® LVAD implantation at Barnes Jewish Hospital, St. Louis, Missouri, USA. Legally acceptable representatives will be able to consent for trial participation.

Exclusion criteria:

Any patient who is unable to receive heparin [e.g. patients with heparin-induced thrombocytopenia (HIT)] or an anaphylactic allergy to heparin] will be excluded. Patients who develop HIT during the course of the study will remain enrolled and be included in the intention-to-treat analysis. Additional exclusions include less than 18 years of age, patients with a known hypercoagulable disorder (factor V Leiden, Antithrombin deficiency, Protein C deficiency, Protein S deficiency, Antiphospholipid antibodies, or other thrombophilia), prisoners, pregnant or lactating women. Also, excluded are patients that are recipients of additional mechanical circulatory support (including extracorporeal membrane oxygenation support, right ventricular assist device, and/or impella) during the index LVAD implantation through the end of the study period.

Recruitment and consent:

Patients will be enrolled during a preoperative clinic visit at our Center for Preoperative Assessment and Planning, from the hospital ward at Barnes-Jewish Hospital, St. Louis, Missouri prior to surgery, or a pre-operative visit at the Ventricular Assist Device Surgery Clinic. Formal consent will be obtained from all participants prior to enrollment in the study. Authorized surrogates will be able to consent for trial participation. Any subject will be free to withdraw their consent at any time.

Interventions

Patients will be randomized to either anti-Xa or aPTT nomograms when the decision is made to start anticoagulation. Patients that receive an additional pumping support device during the index surgery, but prior to randomization will be withdrawn from the study and their baseline data will be discarded. In the rare event the patient receives the assistive pumping device after the index surgery and randomization, they will be withdrawn from the study and the data collected up to that point will be retained for analysis. Consistent with our current heparin management strategy, patients in both arms will be started on a fixed heparin dose (e.g. 750units/hour) on the morning of the first post-operative day. On the second post-operative day, patients will be placed on a

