The potential serious risks attributable to avoiding anticoagulation as well as providing heparin and warfarin anticoagulation are well known and include gastrointestinal bleeding, mediastinal bleeding, retroperitoneal bleeding, stroke, LVAD thrombosis, and potentially death. As these are known and anticipated, they will be reported annually to the IRB. All unexpected adverse events associated with research participation or study intervention will be reported to the WUSTL IRB per their Reportable Event Reporting guidelines [WUSTL IRB Policies and Procedures, Section X]. All safety events, including adverse events and/or laboratory abnormalities identified in the protocol as critical to safety evaluations will be reported to the PI in a timely fashion.

The specific monitoring plan for this investigation is commensurate with the risks and the size and complexity of the investigations planned with this feasibility trial. Should there be an unanticipated serious adverse event that potentially increases the risks to the participants, the study will be stopped, an investigation will be conducted by the PI and research team members, and a findings report will be generated and submitted to IRB before the study is resumed. The safety data will be monitored and reviewed every 3 months.

E Statistical Plan

Sample size:

For the planned feasibility study, we have selected a convenience sample of 20 patients; 10 patients randomized to the anti-Xa monitoring arm and 10 patients randomized to the aPTT monitoring arm. Data collected on subjects that were excluded based on receipt of an additional pumping device during the index surgery but prior to randomization will not be included in the dataset. Data from subjects excluded based on receipt of an additional pumping device after randomization will be retained and analyzed up to the point of withdrawal from the study.

No power analysis is planned for this feasibility trial.

Descriptive statistics will be performed looking at the study groups.

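### The added-support exclusion runs past randomisation, so a later device cuts short a randomised patient's follow-up, which does not fit the stated intention-to-treat approach

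*Combined protocol and SAP*

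**What the plan says.** Section C, Exclusion criteria, lists receipt of additional mechanical circulatory support as an exclusion. The last devices named and the window are: "right ventricular assist device, and/or impella) during the index LVAD implantation through the end of the study period". Section C, Randomization and Design, places randomisation after the implant: "Randomization will take place within twelve hours after arrival to the ICU".

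Two handling rules follow in Section C, Interventions:

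- Patients who receive an extra device during the index surgery and "prior to randomization will be withdrawn from the study and their baseline data will be discarded".
- For patients who receive one after both the index surgery and randomisation, an event the text describes as rare, "they will be withdrawn from the study and the data collected up to that point will be retained for analysis".

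Section E, Sample size, repeats the second rule and calls these patients excluded: "Data from subjects excluded based on receipt of an additional pumping device after randomization will be retained and analyzed up to the point of withdrawal".

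On the analysis principle, Section E says "We will use intent-to-treat approach in our analyses", and the Synopsis says the same. For heparin-induced thrombocytopenia (HIT), another event that can follow randomisation, the Exclusion criteria say: "Patients who develop HIT during the course of the study will remain enrolled and be included in the intention-to-treat analysis".

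**The concern.** Eligibility for a randomised comparison should depend on facts known when the patient is randomised. Here one criterion depends partly on what happens afterwards, and meeting it ends the patient's follow-up.

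The event may not be independent of the outcomes. Section D, Outcomes data, counts heart failure not attributable to structural disease, and abnormal pump parameters, among the criteria for suspected pump thrombosis. Extra support could plausibly follow that kind of deterioration. The documents do not state such a link, so the truncation is possibly informative, not demonstrably so.

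What is at stake is complete outcome information in a small trial: clinical events after the device are not recorded, and some patients may have no value for the primary success measures. Section C also describes this trial as the foundation for a larger pilot and a comparative effectiveness trial, so the rule could be carried forward.

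**Working it through.** The plan has no figure to reproduce here: the sample is a convenience sample of 10 + 10 = 20, with no power analysis and no stated rate of added support. The check is a reading of the text, followed by an illustration of scale.

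**Step 1: the window against randomisation.** The exclusion starts at the index implantation and lasts to the end of the study. Randomisation comes after implantation, within twelve hours of ICU arrival. Part of the window is therefore post-randomisation.

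**Step 2: what happens to each patient.**

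| Time of added device | Handling stated | Consequence |
|---|---|---|
| Index surgery, before randomisation | Withdrawn, data discarded | No breach of intention to treat, since not yet randomised |
| After index surgery, before randomisation | Neither handling rule covers it | Gap |
| After randomisation | Withdrawn, data kept to that point | Follow-up truncated |

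**Step 3: effect on the clinical outcomes.** Section E compares these with a Chi-square test where study size permits. That test makes no allowance for unequal follow-up, so a patient with shortened follow-up and no event so far counts as event-free.

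**Step 4: effect on the success measures.** Section B defines therapeutic anticoagulation as two consecutive in-range values. A patient withdrawn before that point has no time to first therapeutic anticoagulation, no completed count of dosing changes to reach it, and no percentage of time in range after it. Section E plans a t-test or Mann-Whitney test with no censoring rule, and no imputation of primary outcomes. Such a patient drops out of those three comparisons by default.

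**Step 5: scale.** Assume each of 20 randomised patients independently receives a later device with probability p. Expected number = 20p; chance of at least one = 1 − (1 − p)^20. The values of p are assumptions.

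| Assumed p | Expected of 20 | Chance of at least one |
|---|---|---|
| 1% | 0.2 | 1 − 0.99^20 = 18% |
| 2% | 0.4 | 1 − 0.98^20 = 33% |
| 5% | 1.0 | 1 − 0.95^20 = 64% |
| 10% | 2.0 | 1 − 0.90^20 = 88% |

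One patient is 1/10 = 10% of an arm. For example, if one event after withdrawal is missed, a true 3/10 (30%) is reported as 2/10 (20%).

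**Step 6: a missed event needs more than a withdrawal.** It also needs a later event. If, as a further assumption, 30% of withdrawn patients had one, the chance of any missed event is 1 − (1 − 0.3p)^20, which is 6%, 11% and 26% at p = 1%, 2% and 5%.

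**The case against.** The strongest reply is that little is lost. The words excluded and withdrawn might lead a reader to infer that these patients are deleted from the randomised set. They are not: both Section C and Section E keep and analyse their data up to withdrawal. If pump thrombosis or bleeding is what led to the device, that event came first and is counted, and a second event of the same kind would not change a per-patient count. This stands, and it limits the point to truncated follow-up.

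The HIT contrast is also weaker than it looks. Section C, Duration of Study, ends follow-up for everyone when heparin is discontinued, so a patient with HIT who stays enrolled is not promised later outcome collection. The inconsistency in enrolment status is real, but copying the HIT rule would not by itself extend follow-up.

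Finally, this is a feasibility trial without a power analysis. The event is described as rare, the clinical outcomes are exploratory, and stopping nomogram assessment when the heparin regimen may change is a prespecified choice. This stands as a limit on importance. It does not explain why outcome recording must stop as well, and it does not supply the values missing from the success measures.

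**Conclusion.** The point holds as possibly informative truncation of follow-up that does not fit the stated intention-to-treat approach. It is a cheap improvement to make, not a threat to the trial's feasibility aim.

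The expected number of affected patients runs from 0.2 to 2 of 20 across assumed rates of 1% to 10%. The word rare points to the lower end, but the documents give no rate. A missed event lowers the count in the arm where it occurs. Nothing shows which arm would be affected more, so the size and direction of any bias in the comparison are unknown.

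Two further inferences are not supported. A reader might conclude that time in range would favour the arm that lost patients; a shorter observation window could move that percentage either way. A reader might also take the Synopsis target of 20 evaluable patients to mean that withdrawn patients are replaced. No section mentions replacement, and the figure can simply mean the 20 randomised in Section E.

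**What to change.** 1. In Section C, Exclusion criteria, end the window at randomisation, for example: receipt of additional mechanical circulatory support at any time before randomisation. Delete the clause extending it to the end of the study. This also covers a device placed after surgery but before randomisation.
2. In Section C, Interventions, and Section E, Sample size, replace withdrawal of randomised recipients with retention in the assigned arm for analysis. Record the date of the device and the reason for it.
3. Continue chart collection of clinical outcomes for these patients for an explicitly stated period, for example up to the day their planned follow-up would have ended, whatever care the clinical team chooses. State the period directly, because the general follow-up rule stops when heparin stops.
4. Report the nomogram measures with and without data after the added device.

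The cost is wording changes in three places and a few more days of record review for what should be few patients. The downside is that post-device data may reflect a different heparin regimen; the two-way report in item 4 makes that visible.
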